Methodology:	
This is a multinational, multicenter, open-label, single-arm phase II study to evaluate the combination of encorafenib, binimetinib and cetuximab in subjects with BRAF^{V600E} mutant mCRC who have not received any prior systemic therapy for metastatic disease.
 
Subjects will be eligible for the study based on identification of a BRAF^{V600E} mutation in the tumor tissue as determined by local laboratory result obtained at any time prior to Screening. Only polymerase chain reaction (PCR) and next generation sequencing (NGS)-based results will be acceptable. The BRAF mutation status must be confirmed by central laboratory no later than 30 days after the first dose of study treatment. In cases where there is discordance between the local assay and central laboratory results, or if the central laboratory is not able to confirm presence of a BRAF^{V600E} mutation due to inadequate or poor sample condition or insufficient amount of tumor cells in sample within 30 days of initiating study therapy, subjects may only continue treatment if there is no clinical indication of deterioration or disease progression and the Investigator determines that the subject is deriving benefit. In such instances, subjects must be informed that the BRAF mutation status is unconfirmed and must sign a separate informed consent form (ICF) that includes this information and describes alternative treatment options.
 
Main study period design (treatment phase) The Main study period will include two stages according to a two-stage design.
 
Stage 1: In the first stage, 40 subjects will be treated. In case of discordance in the results between the local assay and the central laboratory (potential false-positive local result), or lack of BRAF^{V600E} confirmation, subject will be replaced for the primary analysis of the futility analysis. If there are 11 or fewer confirmed responses (CR or PR) in the 40 treated subjects with a centrally confirmed BRAF^{V600E} mutation, the study will be stopped. Otherwise, additional subjects will enter stage 2. Stage 2 may be initiated as soon as 40 subjects with a centrally confirmed BRAF^{V600E} mutation are treated and confirmed responses are observed in at least 12 subjects.
 
Stage 2: 50 additional subjects will be treated, for a total of 90 subjects with a centrally confirmed BRAF^{V600E} mutation. In case of discordance in the results between the local assay and the central laboratory (potential false-positive local result), or lack of BRAF^{V600E} confirmation, subjects enrolled in the stage two of the trial will be replaced for the primary analysis.
 
If at any time during the study, either in stage 1 or in stage 2, there is discordance between the local assay and the central laboratory in 3 subjects ($\geq 3\%$ of the total targeted 90 treated subjects) or impossibility to confirm the BRAF^{V600E} mutation in 6 subjects ($\geq 6\%$ of the total targeted 90 treated subjects), all subsequent subjects will be required to have BRAF^{V600E} determined by the central laboratory prior to study treatment assignment. For the statistical design, please refer to the statistical section hereunder.
 
Treatment will be administered in 28-day cycles until disease progression, unacceptable toxicity, withdrawal of consent, initiation of subsequent anticancer therapy or death.
 
An independent Data Safety Monitoring Committee (iDSMC) will review the available safety information at regular intervals as defined in the iDSMC charter.
 
Main study period will end, as initially planned, 1 year after the start of study treatment of the last subject enrolled (as the last enrolled subject started study treatment on 27 Dec 2019, Main study period will end on 27 Dec 2020).

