g	
Blood sample for tumor markers (CEA, CA19-9) should be collected only if performed as per clinical routine practice

h	
ECGs scans must be performed every 3 cycles at D1 and at EOT ; and more frequently if clinically indicated during study .
 
ECHO MUGA must be performed every 12 weeks at D1, and at EOT or more frequently if clinically indicated during study

i	
Visual assessment (general inspection of the eyes, examination of motility and alignment, visual disturbance including diminished central vision, blurred vision or loss of vision) to be performed on site by the investigator.
 
Full ophthalmic examination by ophthalmologist to be performed at EOT and, if clinically indicated during treatment, including best corrected visual acuity for distance testing, slit lamp examination, intraocular pressure and dilated funduscopy with attention to retinal abnormalities, OCT and/or fluorescein angiography as appropriate.
 
A full ophthalmic examination at the 30-day FU is only required if there was a clinically significant abnormality noted at EOT

j	
Tumor evaluations to be performed every 12 weeks (±7 days) until disease progression

k	
If a subject discontinues study treatment for reasons other than disease progression, then tumor assessments should continue to be performed (per local and central review) every 12 weeks until the start of new anti-cancer therapy, disease progression, death, lost to follow-up, patient decision, consent withdrawn or study end

l	
For subjects who discontinue study treatment due to disease progression, the survival follow up phase will start after the 30-days safety follow up is complete. The subject will be contacted by phone for collection of information every 3 months.
 
For subjects who discontinue study treatment due to reasons other than disease progression, tumor assessment must be performed until start of new anti cancer therapy,disease progression, death, lost to follow-up, subject’s decision, consent withdrawn or study end.

m	To be performed 30-days after end of treatment (EOT). When clinically appropriate, as per standard of care it is recommended that subjects be monitored for physical examinations, dermatological examinations and chest CT scans for cutaneous and non-cutaneous secondary malignancies for up to 6 months after the last encorafenib dose or until initiation of another antineoplastic therapy.

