8. ASSESSMENTS

8.1. EFFICACY ASSESSMENTS

Tumor response will be evaluated locally by the Investigator according to RECIST, v1.1 (**Section 17.6**).

All potential sites of tumor lesions will be assessed at screening, the following should be performed:

- A CT scan with IV contrast of chest, abdomen and pelvis is the preferred technique. If there is concern about radiation exposure, an MRI may be used instead of a CT.
- In subjects with a history of asymptomatic brain metastases, a brain MRI or CT scan
- If clinically indicated, a whole-body bone scan (i.e., if bone metastases are suspected or known at baseline). A whole-body bone imaging method may be used per local standard of care (e.g., Tc99m bone scan, fluorodeoxyglucose-positron emission tomography [FDG-PET], sodium fluoride-positron emission tomography [NaF PET] scan or whole-body bone MRI).

Skeletal lesions identified on a whole-body bone scan at baseline, which are not visible on the chest, abdomen, or pelvis CT (or MRI) scan should be imaged at baseline using localized CT, MRI, or X-ray.

As far as possible, the same method of assessment of each lesion should be used at screening and for all visits, for consistent comparison.

During the Main study period, all post-screening assessments should be performed every 6 weeks (± 7 days) from the first dose for the first 12 weeks of treatment; except for first tumor evaluation for which the time-window allowed is day 42 ± 7 days from first dose. Then, every 8 weeks thereafter until disease progression, subject decision, withdrawal of consent, initiation of subsequent anticancer therapy, subject is lost to follow-up, death or defined end of study as described in **Section 5.7**.

During the Study extension period, all assessments should be performed every 12 weeks (± 7 days), until disease progression, subject decision, withdrawal of consent, initiation of subsequent

anticancer therapy, subject is lost to follow-up, death or defined end of study as described in **Section 5.7**.

If a subject discontinues study treatment for reasons other than disease progression, tumor assessments must continue to be performed (as per local and central review) every 6 weeks (first 12 weeks) then every 8 weeks during the Main study period and every 12 weeks during the Study extension period (as per local review), until the start of new anti-cancer therapy, disease progression, death, lost to follow-up, subject decision or withdrawal consent.

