9.1.6. Subsequent Cycles _ Main study period

Tumor assessments (i.e., appropriate radiological scans to document all suspected sites of disease) are to be performed every 6 weeks (± 7 days) from the first dose for the first 12 weeks, then every 8 weeks (± 7 days) thereafter until disease progression, subject decision, withdrawal of consent, initiation of subsequent anticancer therapy, subject is lost to follow-up, or death, regardless of whether study treatment is discontinued.

The time-window allowed for the first tumor assessment (i.e. day 42 from first dose) is +7 days. Information on Healthcare Resource Utilization will be obtain in case of hospitalization and during the whole treatment period until 30 days after the last administration of study treatment. (see **Section 8.7**)

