13. STATISTICAL ANALYSIS

13.1. GENERAL CONSIDERATIONS

A detailed statistical analysis plan (SAP) will be prepared by the Sponsor. This plan may modify the statistical methods outlined in the protocol; however, any major modifications related to the primary outcome measure definition or analysis will also be described in a protocol amendment.

The statistical analysis will be done under the supervision of the study statistician at the Biometry Department, IRPF. Analyses will be programmed in accordance with the SAP.

The CSR is planned to be written at the time of the primary outcome measure analysis (after Stage 1 if the study is stopped for futility, otherwise after Stage 2).

The cut-off date for futility analysis and Stage 2 analysis is estimated to occur approximately when all treated subjects with a centrally confirmed *BRAF*^{V600E} mutation of the concerned stage have either discontinued or have four post-baseline tumor assessments. And in case the last subject required for the concerned stage has an objective response, it should be confirmed in the following tumor assessment before the analysis is being performed. However, it will be possible to proceed to Stage 2 as soon as 40 subjects with a centrally confirmed *BRAF*^{V600E} mutation are treated and 12 confirmed responses are observed.

All available data will be included at the time of the cut-off date for secondary time-to-event endpoints and safety assessments. Unless the study is stopped at an earlier point in time, any further CSR update (or addendum) will be written at the end of study.

After the primary outcome measure analysis (after Stage 1 if the study is stopped for futility, otherwise after Stage 2), an analysis will be performed at the end of the Main study period, and at the end of the Study extension period).

Descriptive methods will be used to present all relevant data:

- Continuous data will be summarized with: frequency, median, range, mean, standard deviation and standard error if relevant.
- Categorical data will be presented in contingency tables with frequencies and percentages of each modality.

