13.8.2. Analysis of Secondary Outcome Measures

The cORR based on central review, and ORR (for confirmed + unconfirmed responses) based on local radiologist/investigator-assessed tumor evaluations and central radiologist review will be provided with a corresponding Clopper-Pearson (exact) binomial 95% CI for the ES and FAS.

The Kaplan-Meier (KM) method used to describe OS will present median time with 95% CI and estimates at several time points (including 2, 4, 6, 8, 10 and 12 months). Subjects without a death date by the data cut-off date will be censored for OS at their last contact date.

PFS will be calculated for the FAS and summarized using the KM method. The corresponding median PFS as well as PFS rates at selected time points (e.g. 3 and 6 months) will be provided with a 95% CI.

Progressive disease and death from any cause will be considered as events. If death or PD is not observed, the PFS will be censored at the date of last adequate tumor assessment prior to the cutoff date. However, if a PFS event is observed after more than 1 missing or inadequate tumor assessment, it will be censored at the last adequate tumor assessment. If a PFS event is observed after a single missing or non-adequate tumor assessment, the actual date of event will be used.

Subjects who received a new anti-tumoral treatment (chemotherapy, hormonotherapy, radiotherapy, surgery or other anti tumoral treatment), whatever the type of treatment before their disease progression will be censored at the last adequate assessment prior to the start date of the new antitumoral treatment.

Additional sensitivity analyses examining alternative censoring rules could be applied and will be described in the SAP.

Analysis of DOR and TTR will be summarized using KM method in a similar way.

Secondary outcomes measures in the subgroup of Japanese subjects will be examined separately.

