**This rule will be based on the distance between the last adequate TA date and the event date.**

Let D1 be the largest distance (relative to the last adequate TA date) that a patient can have a tumor assessment and not be classified as having missed an assessment. Let D2 be the largest distance (relative to the last adequate TA date) that a patient can have a tumor assessment and not be classified as having missed two assessments. If the distance exceeds threshold D1 or D2 then the analysis will assume one or two missing TAs, respectively.

The threshold D1 will be defined as the protocol specified interval between the TAs plus the protocol allowed window around the assessments. Similarly, the threshold D2 is defined as two

times the protocol specified interval between the TAs plus the protocol allowed window around the assessments.

As per protocol, post-screening assessments are expected to be performed every  $A=6$  weeks ( $\pm B=7$  days) from the first dose for the first 12 weeks of treatment ( $I=84$  days); except for first tumor evaluation for which the time-window allowed is day 42 +7 days from first dose, then every  $X=8$  weeks ( $\pm Y=7$  days) thereafter until disease progression, subject decision, withdrawal of consent, initiation of subsequent anticancer therapy, subject is lost to follow-up, death or defined end of study.

Therefore:

- if the last adequate tumor assessment before the event date is performed on or before study day 21 ( $=7*A/2$ ) then  $D_1=49 (=A*7+B)$  days and  $D_2=91 (=2*A*7+B)$  days;
  - This accounts for the scenario where the last adequate tumor assessment is the baseline assessment. This also allows for the rare instance where an additional assessment occurred early in the study.
- if the last adequate tumor assessment before the event date is performed between study day  $M+1$  (where  $M= I- (1.5*A)*7$ ) to study day  $N$  then  $D_1=A*7+2*B$  days and  $D_2=(A+X)*7+B+Y$  days;
  - Day  $N$  is calculated as  $N = I- (0.5*A)*7$ .
  - This accounts for the scenario where only the first scheduled assessments after the last adequate tumor assessment occur prior to month  $I$ .
- if the last adequate tumor assessment before the event date is performed between study day  $N+1$  and study day  $P$  then  $D_1=X*7+B+Y$  days and  $D_2=2*X*7+B+Y$  days;
  - Day  $P$  is calculated as  $P = I+ (0.5*X)*7$ .

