  - This accounts for the scenario where only the last adequate tumor assessment occurs prior to month  $I/7$ .
- otherwise, when the last adequate tumor assessment before the event date is performed after study day  $P+1$ , then  $D_1=X*7+2*Y$  days and  $D_2=2*X*7+2*Y$  days.

Using the D2 definition above, an event is censored as occurring after  $\geq 2$  missing tumor assessments if the distance between the last adequate tumor assessment date and the event date is larger than D2.

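### The SAP's missed-scan threshold assumes 8-week scans; if applied to the 12-week extension schedule, it censors some PFS and DOR events after a single missed scan as if two had been missed

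*SAP*

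**What the plan says.** **The missed-scan rule.** SAP 9.3 defines D1 and D2 as one or two times the protocol's scan interval plus the allowed window. It then fixes that interval: "post-screening assessments are expected to be performed every" 6 weeks for the first 12 weeks, then every 8 weeks. Table 8 gives D1/D2 of 49/91, 56/112 and 70/126 days for a last adequate scan on study days 1–21, 22–63 and 64 or later. The text behind the last row ends with an open-ended case, "otherwise, when the last adequate tumor assessment before the event date is performed after study day" P+1, which uses the 8-week interval with no later change. An event further than D2 from the last adequate scan is treated as following two or more missed scans and is censored at that scan.

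**The single-miss principle.** Protocol 13.8.2 censors only after more than one miss: "if a PFS event is observed after more than 1 missing or inadequate tumor assessment, it will be censored at the last adequate tumor assessment". It and SAP 14.2.4 both count an event after a single miss at its actual date. Tables 12 (rows C1, C2) and 14 (rows A1, A2) carry this into PFS and DOR. For DOR, only deaths due to underlying disease are events.

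**The schedule.** Protocol 9.1.6 matches the SAP for the main period: "then every 8 weeks (± 7 days) thereafter until disease progression". Protocol 8.1 then changes it: "During the Study extension period, all assessments should be performed every 12 weeks". Footnote j of the extension flow-chart agrees: "Tumor evaluations to be performed every 12 weeks (±7 days) until disease progression". The extension starts on 28 December 2020.

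**The analyses.** After the primary analysis, Protocol 13.1 states that "an analysis will be performed at the end of the Main study period, and at the end of the Study extension period". Protocol 13.2.2 bases extension endpoints on local review. SAP 6.6 lists three analyses (Stage 1, Stage 2, end of study) and does not mention the extension.

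**The concern.** The threshold is meant to separate one missed scan from two, and it can do so only if its interval is the one that subjects actually follow. In the extension they follow 12 weeks while the rule still counts in units of 8. The gap left by one missed extension scan is then read as two missed scans, and an event that the plan intends to count becomes a censored observation dated at the last adequate scan.

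Subjects still being scanned in the extension are the long-term progression-free ones who determine the late part of the PFS and DOR curves. Removing their events raises those curves from the event date onward.

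**Working it through.** **Reproducing Table 8.** Inputs from SAP 9.3: A = 6 weeks, B = 7 days, I = 84 days, X = 8 weeks, Y = 7 days. The cut-points are M = 84 − 63 = 21, N = 84 − 21 = 63 and P = 84 + 28 = 112.

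- Days 1–21: D1 = 42 + 7 = 49; D2 = 84 + 7 = 91.
- Days 22–63: D1 = 42 + 14 = 56; D2 = 14 × 7 + 14 = 112.
- Day 64 on: D1 = 56 + 14 = 70; D2 = 112 + 14 = 126.

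All three rows match the printed table.

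**Which row applies.** The protocol synopsis says that "the last enrolled subject started study treatment on 27 Dec 2019". Every subject is therefore more than a year past first dose when the extension opens, and the relevant last scans fall in the last row, with D2 = 126.

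**Gap to the next scheduled scan.** With ±7 days at each end, the gap is 7 × (weeks between the scans) ± 14 days.

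| Situation | Weeks | Gap (days) | Whole-day gaps above 126 |
|---|---|---|---|
| Main period, one missed | 16 | 98–126 | 0 of 29 |
| Main period, two missed | 24 | 154–182 | 29 of 29 |
| Extension, none missed | 12 | 70–98 | 0 of 29 |
| Extension, one missed | 24 | 154–182 | 29 of 29 |
| Transition (8 + 12), one missed | 20 | 126–154 | 28 of 29 |

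In the main period the rule works as intended. In the extension, one missed scan leaves exactly the gap that two missed scans leave on the 8-week schedule.

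**Events that survive.** Protocol 8.1 allows imaging at any time when progression is suspected. With the day-84 scan missed, an event on days 85 to 126 is still counted. That is 126 − 84 = 42 of the 84 days before the next scan is due. A death after day 126, with only one scan missed, is censored.

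**D1.** A punctual extension scan usually exceeds D1 = 70 (28 of 29 gaps) and is labelled as one missed. Zero and one missed are handled alike in Tables 12 and 14, so no PFS or DOR outcome changes.

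**Size.** The documents give neither the number of subjects in the extension nor the rate of missed scans. As an assumption only: with n subjects at risk, one counted event multiplies the Kaplan–Meier estimate by 1 − 1/n, whereas a censored one leaves it unchanged. The lost factor is 0.80 for n = 5, 0.90 for n = 10 and 0.95 for n = 20.

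**The case against.** The strongest reply is that the SAP rule was never written for extension data. SAP 6.6 ends the study one year after the last subject's first dose, which is 27 December 2020, the day before the 12-week schedule begins. For every analysis up to then, D1 and D2 match the schedule in force. The general definition refers to the protocol's interval, so a later plan could substitute 12 weeks without changing the principle. This makes the consequence conditional, and it stands to that extent.

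It does not close the gap. Protocol 13.1 requires an end-of-extension analysis. Protocol 15.3.1 places the end of study when all treated subjects have progressed or discontinued, and SAP 14.2.4 repeats PFS at the end of study. The protocol is version 9.0 of 17 July 2020. SAP version 4 was revised until November 2020 and version 5 is dated 22 January 2021, yet SAP 9.3 is still the only missed-scan rule. Either it is carried over and miscensors, or the extension analysis has no rule.

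The effect on reported PFS is also limited. The Table 13 sensitivity analysis keeps these events. For the last subject enrolled, 28 December 2020 is study day 368. A progression at the scheduled scan after a missed extension scan comes no earlier than day 368 + 84 − 7 = 445, or 445/30.4375 = 14.6 months, beyond the 14 months to which SAP 14.2.4 tabulates PFS probabilities. DOR is less protected. It has no such sensitivity analysis and runs from first response. With a response at the day-42 scan, the same event gives 445 − 42 + 1 = 404 days, or 13.3 months, inside the tabulated range.

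A reader might infer that every progression after one missed extension scan is censored. The documents do not support that: progression found by unscheduled or late imaging up to day 126 remains an event, as does a death in that time that meets the endpoint's definition.

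**Conclusion.** The point holds conditionally. If SAP 9.3 is applied unchanged at the end of the extension, two kinds of event are censored against the plan's single-miss rule:

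- a progression first found at the next scheduled scan after one missed or non-evaluable extension scan (154–182 days after the last adequate scan);
- a death more than 126 days after the last adequate scan with only one scan missed (for DOR, a death due to underlying disease).

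The bias in late PFS and DOR is upward; its size is unknown.

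This assumes that the end-of-extension analysis includes PFS and DOR, since Protocol 13.1 does not list its endpoints, and that no other missed-scan rule exists outside these documents.

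It would be wrong to infer a threat to the trial's main conclusion. cORR and the Stage 1, Stage 2 and end-of-main-period results are untouched, and SAP section 8 treats everything beyond the primary test as exploratory. The matter should be corrected before the extension analysis, but does not bear on the primary result.

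**What to change.** For the end-of-extension PFS and DOR analysis, make the thresholds follow the scan interval in force after the last adequate scan:

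- both following intervals 8 weeks: D2 = 126 days, as now;
- one of 8 and one of 12 weeks: D2 = 56 + 84 + 14 = 154 days;
- both 12 weeks: D2 = 2 × 84 + 14 = 182 days;
- for consistent labelling, D1 = 84 + 14 = 98 days when the next interval is 12 weeks.

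At 182 days, one missed extension scan (154–182) is kept and two missed (36 weeks, 238–266 days) are censored. The switch must depend on calendar date. Table 8 is indexed by study day, and 28 December 2020 is a different study day for each subject, so extra study-day rows would not work.

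Two clarifications are needed alongside. The protocol should state whether the first extension scan is due 8 or 12 weeks after the last main-period scan, because that decides which threshold applies at the transition. SAP 6.6 and the SAP's end-of-study definition should be reconciled with Protocol 13.1 and 15.3.1, so that the extension analysis and its endpoints are specified.

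The cost is a SAP amendment, a protocol clarification and a date-dependent derivation in the programs. No new data are needed.
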